### 15.2. Stratification Factors

No stratification is planned.

### 15.3. Interim Analyses

In Phase 2a, Arms I, II, III, IV, and V will have a futility interim analysis per the Simon's two-stage minimax design at 17 evaluable subjects based on ORR assessed by RECIST 1.1 and

iRECIST. In Phase 1b there is a safety interim analysis after each dose level to determine the dosing for the next subject.

An interim analysis will not be performed for IVa, Va, and the Biomarker Cohort Ovarian Cancer.

#### **15.4. Data Monitoring Committee (DMC)**

To provide oversight of safety, efficacy, and study conduct, a Data Monitoring Committee (DMC) will be instituted. The voting members of the committee are external to the Sponsor. They must not be involved with the trial in any way (e.g., trial` investigators) and must not have competing interests that could affect their roles with respect to the trial.

The DMC will monitor for subject safety and scientific integrity during the study. The DMC will make a decision for dose escalation or dose-de-escalation in the Phase 1b and determine the RP2D; in Phase 2a and Biomarker Cohort. The DMC will monitor for subject safety and scientific integrity during the study. The DMC will meet to review the safety and efficacy data at the interim analysis for arms I, II, III, IV, and V (i.e., after the 17th evaluable subject enrolled into the arm has had the 1st tumor assessment). At intervals defined by the DMC charter, the DMC will review and evaluate the data on clinical efficacy and safety collected during the study and assesses reports on cumulated SAEs. In addition to the pre-scheduled data reviews and planned safety monitoring, the DMC will convene additional ad hoc meetings to conduct emergency reviews of any event that potentially impacts safety at the request of the sponsor. Following each meeting, the DMC will recommend continuation, modification, or discontinuation of the study based on observed toxicities.

Specific details regarding composition, responsibilities, and governance, including the roles and responsibilities of various members and the Sponsor protocol team; meeting facilitation; the trial governance structure; and requirements for and proper documentation of DMC reports, minutes, and recommendations will be described in a separate charter that is reviewed and approved by the DMC.

#### **15.5. Statistical Analysis Plan Summary**

Study Design Overview	An Open-label Phase 1b/2a Study of NT-I7 (efineptakin alfa) in Combination with Pembrolizumab in Subjects with Relapsed/Refractory Advanced Solid Tumors
Analysis Populations	Safety: All-Subjects-as-Treated (ASaT) PK: Per-Protocol (PP) Efficacy: All evaluable per arm, a subset may be repeated on All-Subjects-as-Treated (ASaT).

	Descriptive analysis will be performed at the end of enrollment for Arms IVa and Va.
Primary Endpoint(s)	
Phase 1b:
 
 
Incidence, nature, and severity of adverse events graded according to NCI CTCAE v5.0
 
Incidence and nature of DLTs
 
Potential correlation of dose levels with safety and efficacy parameters
 
 
Phase 2a:
 
 
Objective Response Rate (ORR) for each individual arm, defined as the percentage of subjects who have at least one confirmed partial response (PR) or complete response (CR), per RECIST 1.1 and iRECIST as determined by the investigator
 
 
Biomarker Cohort:
 
 
To assess a potential correlation between tumor infiltrating lymphocytes (TILs) and clinical benefits in subjects with CPI-naïve R/R OC.
 

Secondary Endpoints	
Phase 1b/2a:
 
 
Duration of objective response (DOR) for each individual arm, defined as the time from the first occurrence of a documented objective response to the time of the first documented disease progression or death from any cause, whichever occurs first, per RECIST 1.1 and iRECIST as determined by the investigator.
 
Disease Control Rate (DCR) for each individual arm, defined as proportion of subjects with a best overall response of CR, PR or stable disease (SD), per RECIST 1.1 as determined by the investigator.
 
Progression Free Survival (PFS) for each individual arm, defined as the time from the first study treatment (Cycle 1, Day 1) to the first occurrence of progression or death from any cause, whichever occurs first, per RECIST 1.1 as determined by the investigator.
 
Overall survival (OS) for each individual arm, defined as the time from first study treatment (Cycle 1, Day 1) to death from any cause
 
Incidence of anti-drug antibody (ADA) to NT-I7 during the study relative to the prevalence of ADA at baseline
 

	
Biomarker Cohort:
 
 
• To assess the safety and tolerability of NT-I7 in combination with pembrolizumab in subjects with CPI-naïve R/R OC
 

Statistical Methods for Efficacy Analysis	
Primary: ORR will be considered a primary efficacy endpoint and estimated using exact confidence intervals based on the binomial distribution (Clopper-Pearson intervals). A test from the Simon minimax design for null hypothesis ORR proportion in the arm population 4% vs alternative hypothesis 21% will be conducted in each arm at 1-sided alpha = 0.025 and the p-value reported.
 
Arms I, II, III, IV, and V for the Phase 2a study stage will follow the Simon's two-stage minimax design in each arm and has 5 arms. Each arm will enroll 17 evaluable subjects in Stage 1 and, if the Go/No Go criterion is met, an additional 8 evaluable subjects in Stage 2 for a total of 25 evaluable subjects/arm. Exact 95% binomial Clopper-Pearson confidence interval estimates of ORR for arms I, II, III, IV, and V are planned to support the primary hypothesis tests. Enrolment of up to 30 subjects per arm is planned to account for non-evaluable subjects and dropouts. Approximately 210 subjects are planned for the Phase 2a study stage.
 
Note: In addition to the primary analyses on the population of evaluable subjects for the primary endpoint, exploratory analyses will also be presented on the population of all subjects enrolled and treated on study.
 
Secondary:
 
 
• Duration of response (DoR) for the responders in each individual arm, is defined as the time from the first occurrence of a documented objective response to the time of the first documented disease progression or death from any cause, whichever occurs first, per RECIST 1.1 as determined by the investigator. DoR will be assessed statistically via Kaplan-Meier methods and presented descriptively for the responders. Comparative assessments are not planned on this endpoint.
 
• Disease Control Rate (DCR) for each individual arm, is defined as proportion of subjects with a best overall response of CR, PR or SD, per RECIST 1.1 as determined by the investigator. DCR will be assessed statistically via Fisher Exact tests supported by Clopper-Pearson confidence intervals; all analyses will be interpreted descriptively. Comparative assessments are not planned on this endpoint.
 
• Progression Free Survival (PFS) for each individual arm, is defined as the time from the first study treatment (Cycle 1, Day 1) to the first occurrence of progression or death from any cause,
 


	
whichever occurs first, per RECIST 1.1 as determined by the investigator.
 
PFS will be assessed statistically via Kaplan-Meier methods and presented descriptively for all treated patients in each study arm; censoring rules and statistical endpoint definitions (time to event) will be detailed in the SAP prospectively. Comparative assessments are not planned on this endpoint.
 
 
Overall survival (OS) for each individual arm, is defined as the time from first study treatment (Cycle 1, Day 1) to death from any cause.
 
OS will be assessed statistically similarly to PFS (above).
 
Incidence of anti-drug antibody (ADA) to NT-I7 during the study will be assessed, relative to the prevalence of ADA at baseline. Immunogenicity to NT-I7 will be measured using a risk-based, tiered testing approach. Additional details are provided in Table 1.
 

Treatment Assignment	This is not a randomized study.
Statistical Methods for Safety Analyses	Summary statistics will be provided for the safety endpoints as appropriate.
Interim Analyses	
For Phase 2a, Arms I, II, III, IV, and V, an interim analysis for futility is included, per the Simon minimax design.
 
An interim analysis will not be performed for Arms IVa, Va, and the Biomarker Cohort Ovarian Cancer.
 
An interim analysis for Phase 1b will be performed.

Multiplicity	No multiplicity adjustment is planned.
Sample Size and Power	
Up to 238 subjects (up to 18 subjects in the Phase 1b, up to 210 subjects in the Phase 2a and up to 10 subjects in the Biomarker Cohort) are planned to be enrolled in the study.
 
This will provide an estimated 80% power per selected arm in the Phase 2a stage of the study for the primary hypothesis test using the Simon minimax design, for 4% vs 21% ORR, at 1-sided alpha = 0.025, as well as approximately 25 evaluable subjects per arms for 95% exact binomial Clopper-Pearson confidence intervals for ORR from the design (per arm).

**NIT-110**  
**(KEYNOTE PNA60)**  
**V7.0 incorporating Amendment 6, 26Oct2023**

## 17. Abbreviations

ADA	Anti-Drug Antibody
AEs	Adverse Events
AESI	Adverse Event of Special Interest
ALK	Anaplastic lymphoma kinase
ALT	Alanine Amino Transferase
AML	Acute Myelocytic Leukemia
ANC	Absolute Neutrophil Count
aPTT	Activated Partial Thromboplastin Time
ASCO-CAP	American Society of Clinical Oncology – College of American Pathologists
AST	Aspartate Amino Transferase
BCG	Bacillus Calmette–Guérin
BICR	Blinded Independent Central Review
BRAF	Proto-oncogene B-Raf
BUN	Blood Urea Nitrogen
CBC	Complete Blood Count
CD	Cluster of Differentiation
CDASH	Clinical Data Acquisition Standards Harmonization
CFR	Code of Federal Regulation
CHO	Chinese Hamster Ovary
CI	Confidence Interval
CISH	Chromogenic in situ hybridization
CNS	Central Nervous System
CPI	Check Point Inhibitor
CR	Complete Response
CRC	Colorectal Cancer
CrCl	Creatinine Clearance
CRF	Case Report Form
CSR	Clinical Study Report
CT	Computed Tomography
CTEP	Cancer Therapy Evaluation Program
CxDx	Cycle x Day x
D1	Day 1
DCR	Disease Control Rate
DILI	Drug-Induced Liver Injury
DL	Dose Level
DLT	Dose Limiting Toxicity
DMC	Data Monitoring Committee
dMMR	deficient Mismatch Repair
DOR	Duration of Response
ECI	Events of Clinical Interest

ECOG	Eastern Cooperative Oncology Group
EDC	Electronic Data Capture
EGFR	Epidermal growth factor receptor
EKG	Electrocardiogram
EOT	End of Treatment
ER	Estrogen Receptor
FDA	Food and Drug Administration
FDAAA	Food and Drug Administration Amendments Act
FDAMA	Food and Drug Administration Modernization Act
FFPE	Formalin-fixed, paraffin embedded
FISH	Fluorescence in situ hybridization
FT3/FT4	free Triiodothyronine/ free Thyroxine
FU	Follow Up
GCP	Good Clinical Practice
HER2	Human epidermal growth factor receptor 2
HIPAA	Health Insurance Portability and Accountability Act
HIV	Human Immunodeficiency Virus
HR	Hazard Ratio
hyFc	hybrid Fc
ICF	Informed Consent Form
ICH	International Council for Harmonization
iCPD	iRECIST Confirmed Progressive Disease
iCR	iRECIST Complete Response
IDMC	Independent Data Monitoring Committee
IHC	Immunohistochemistry
IM	Intramuscular
IME	Important Medical Events
IND/IDE	Investigational New Drug Application/Investigational Device Exemption
INR	International Normalized Ratio
iPD	iRECIST Progressive Disease
iPR	iRECIST Partial Response
IRB	Institutional Review Board
iRC	Immune-Related Response Criteria
iRECIST	modified Response Evaluation Criteria in Solid Tumors
iSD	iRECIST Stable Disease
ITT	Intent-To-Treat
iUPD	iRECIST Unconfirmed Progressive Disease
IV	Intravenous
LDH	Lactate Dehydrogenase
LLN/ULN	Lower Limit of Normal/Upper Limit of Normal
mAb	Monoclonal Antibody
MDS	Myelodysplastic Syndrome
MED	Maximum Effective Dose

MRI	Magnetic Resonance Imaging
MSI-H	Microsatellite Instability High
MSS-CRC	Microsatellite Stable Colorectal Cancer
MTD	Maximum Tolerated Dose
Nab	Neutralizing Antibody
NCI-CTCAE	National Cancer Institute – Common Terminology Criteria for Adverse Events
NIT	NeoImmuneTech, Inc.
NKT	Natural Killer-T cells
NSAID	Nonsteroidal Anti-Inflammatory Drugs
NSCLC	Non-small Cell Lung Cancer
NT-I7	rh-IL-7-hyFc ka GX-I7
OC	Ovarian Cancer
ORR	Objective Response Rate
OS	Overall Survival
PC	Pancreatic Cancer
PCR	Polymerase Chain Reaction
PD	Pharmacodynamics
PD	Progressive Disease
PD-1/PD-L1	Programmed cell death protein 1/Programmed cell death protein - Ligand 1
PFS	Progression Free Survival
Ph. EUR	European Pharmacopeia
PI	Principal Investigator
PK	Pharmacokinetics
pMMR	proficient Mismatch Repair
PR	Partial Response
PR	Progesterone Receptor
Q3W	Every 3 weeks
Q6W	Every 6 weeks
QTc	Corrected QT interval
R/R	Relapsed/Refractory
RBC	Red Blood Cells
RECIST	Response Evaluation Criteria in Solid Tumors
ROS1	ROS Proto-Oncogene 1
RP2D	Recommended Phase 2 Dose
RP-HPLC	Reverse-Phase High-Performance Liquid Chromatography
SAEs	Serious Adverse Events
SAP	Statistical Analysis Plan
SC	Subcutaneous
SD	Stable Disease
SE-UHPLC	Size-Exclusion Ultra-High-Performance Liquid Chromatography
SGOT	Serum Glutamic-Oxaloacetic Transaminase
SGPT	Serum Glutamic-Pyruvate Transaminase
SOC	System Organ Class

T1DM	Type 1 Diabetes Mellitus
TBL	Total bilirubin level
TEAE	Treatment Emergent Adverse Event
TIL	Tumor-infiltrating lymphocyte
TKI	Tyrosine Kinase Inhibitor
TNBC	Triple Negative Breast Cancer
TNF	Tumor Necrosis Factor
TSH	Thyroid Stimulating Hormone
Tx	Treatment
VOP	Verification of Progression
WBC	White Blood Cells

## Appendix A – Assessment of Disease

### RECIST 1.1 Assessment of Disease

RECIST 1.1 will be used as the primary measure for assessment of tumor response, date of disease progression, and as a basis for all protocol guidelines related to disease status (e.g., discontinuation of study treatment). RECIST 1.1 references a maximum of 5 target lesions in total, and 2 per organ. ([87](#))

### iRECIST Assessment of Disease

iRECIST is based on RECIST 1.1 but adapted to account for the unique tumor response seen with immunotherapeutic drugs. iRECIST will be used by the Investigator to assess tumor response and progression and make treatment decisions. When clinically stable, subjects may continue study intervention beyond RECIST 1.1 progression with continued assessment of response according to the rules outlined in [Table 6](#). iRECIST reflects that some subjects can have a transient tumor flare in the first few months after the start of immunotherapy, and then experience subsequent disease response. This data will be captured in the clinical database.

- If subject is clinically stable, continue study intervention per protocol
  - Perform scans 4 to 8 weeks after RECIST 1.1 progression
  - Continue investigator assessment per iRECIST
- If the subject is not clinically stable, best medical practice is to be applied.

For the purpose of this decision process, lack of clinical stability is defined as:

- Unacceptable toxicity
- Clinical signs or symptoms indicating clinically significant disease progression
- Decline in performance status
- Rapid disease progression or threat to vital organs or critical anatomical sites (e.g., CNS metastasis, respiratory failure due to tumor compression, spinal cord compression) requiring urgent alternative medical intervention.

Any subject deemed **clinically unstable** should be discontinued from study treatment at site-assessed first radiologic evidence of PD and is not required to have repeat tumor imaging for confirmation of PD by iRECIST.

[figure not shown]
If the Investigator decides to continue treatment, the subject should continue to receive study treatment. Regardless of the subject is on treatment or off treatment, the tumor assessment should be repeated 4 to 8 weeks later to confirm PD by iRECIST, per Investigator assessment.

If repeat imaging does not confirm PD per iRECIST, as assessed by the Investigator, and the subject continues to be clinically stable, study treatment may continue and follow the regular imaging schedule. If PD is confirmed, subjects will be discontinued from study treatment.

If a subject has confirmed radiographic progression (iCPD) as defined in [Table 6](#), study treatment should be discontinued; however, if the subject is achieving a clinically meaningful benefit, an exception to continue study treatment may be considered following consultation with the Sponsor. In this case, if study treatment is continued, tumor imaging should continue to be performed following the intervals as outlined in [Table 6](#).

A description of the adaptations and iRECIST process is provided in the latter half of Appendix A – Assessment of Disease, with additional details in the iRECIST publication. A summary of imaging and treatment requirements after first radiologic evidence of progression is provided in [Table 6](#) and illustrated as a flowchart in [Figure 5](#).

**Figure 5: Imaging and treatment for clinically stable subjects treated with NT-I7+pembrolizumab after first radiologic evidence of PD assessed by the investigator.**

**Table 6: Imaging and treatment after first radiologic evidence of progressive disease**

	Clinically Stable		Clinically Unstable	
	Imaging	Treatment	Imaging	Treatment
First radiologic evidence of PD by RECIST 1.1	Repeat imaging at 4 to 8 weeks to confirm PD.	May continue study treatment at the Investigator's discretion while awaiting confirmatory tumor imaging by site by iRECIST.	Repeat imaging at 4 to 8 weeks to confirm PD per Investigator's discretion only.	Discontinue treatment
Repeat tumor imaging confirms PD (iCPD) by iRECIST per Investigator assessment	No additional imaging required.	Discontinue treatment (exception is possible upon consultation with Sponsor).	No additional imaging required.	Not applicable
Repeat tumor imaging shows iUPD by iRECIST per Investigator assessment	Repeat imaging at 4 to 8 weeks to confirm PD. May occur at next regularly scheduled imaging visit.	Continue study treatment at the Investigator's discretion.	Repeat imaging at 4 to 8 weeks to confirm PD per Investigator's discretion only.	Discontinue treatment
Repeat tumor imaging shows iSD, iPR, or iCR by iRECIST per Investigator assessment.	Continue regularly scheduled imaging assessments.	Continue study treatment at the Investigator's discretion.	Continue regularly scheduled imaging assessments.	May restart study treatment if condition has improved and/or clinically stable per Investigator's discretion. Next tumor imaging should occur according to the regular imaging schedule.

iCPD = iRECIST confirmed progressive disease; iCR = iRECIST complete response; iRECIST = modified Response Evaluation Criteria in Solid Tumors 1.1 for immune-based therapeutics; iSD = iRECIST stable disease; iUPD = iRECIST unconfirmed progressive disease; PD = progressive disease; RECIST 1.1 = Response Evaluation Criteria in Solid Tumors 1.1.; VOP=verification of progression

## RECIST 1.1 and iRECIST

### *Assessment at Screening and Prior to RECIST 1.1 Progression*

Until radiographic disease progression based on RECIST 1.1, there is no distinct iRECIST assessment.

### *Assessment and Decision at RECIST 1.1 Progression*

For subjects who show evidence of radiological PD by RECIST 1.1 as determined by the Investigator, the Investigator will decide whether to continue a subject on study treatment until repeat imaging is obtained (using iRECIST for subject management (see [Table 6](#) and [Figure 5](#))). This decision by the Investigator should be based on the subject's overall clinical condition. Clinical stability is defined as the following:

- Absence of symptoms and signs indicating clinically significant progression of disease
- No decline in ECOG performance status
- No requirements for intensified management, including increased analgesia, radiation, or other palliative care

Any subject deemed **clinically unstable** should be discontinued from study treatment at site-assessed first radiologic evidence of PD and is not required to have repeat tumor imaging for confirmation of PD by iRECIST.

If the Investigator decides to continue treatment, the subject may continue to receive study treatment and the tumor assessment should be repeated 4 to 8 weeks later to confirm PD by iRECIST, per Investigator assessment.

Tumor flare may manifest as any factor causing radiographic progression per RECIST 1.1, including:

- Increase in the sum of diameters of target lesion(s) identified at baseline to  $\geq 20\%$  and  $\geq 5$  mm from nadir
  - **Note:** the iRECIST publication uses the terminology “sum of measurements”, but “sum of diameters” will be used in this protocol, consistent with the original RECIST 1.1 terminology.
- Unequivocal progression of non-target lesion(s) identified at baseline
- Development of new lesion(s)

iRECIST defines new response categories, including iUPD (unconfirmed progressive disease) and iCPD (confirmed progressive disease). For purposes of iRECIST assessment, the first visit showing progression according to RECIST 1.1 will be assigned a visit (overall) response of iUPD, regardless of which factors caused the progression.

At this visit, target and non-target lesions identified at baseline by RECIST 1.1 will be assessed as usual.

New lesions will be classified as measurable or non-measurable, using the same size thresholds and rules as for baseline lesion assessment in RECIST 1.1. From measurable new lesions, up to 5 lesions total (up to 2 per organ), may be selected as New Lesions – Target. The sum of diameters of these lesions will be calculated and kept distinct from the sum of diameters for target lesions at baseline. All other new lesions will be followed qualitatively as New Lesions – Non-target.

#### *Assessment at the Confirmatory Imaging*

On the confirmatory imaging, the subject will be classified as progression confirmed (with an overall response of iCPD), or as showing persistent unconfirmed progression (with an overall response of iUPD), or as showing disease stability or response (iSD/iPR/iCR).

#### *Confirmation of Progression*

Progression is considered confirmed, and the overall response will be iCPD, if ANY of the following occurs:

- Any of the factors that were the basis for the initial iUPD show worsening
  - For target lesions, worsening is a further increase in the sum of diameters of  $\geq 5$  mm, compared to any prior iUPD time point
  - For non-target lesions, worsening is any significant growth in lesions overall, compared to a prior iUPD time point; this does not have to meet the “unequivocal” standard of RECIST 1.1
  - For new lesions, worsening is any of these:
    - An increase in the new lesion sum of diameters by  $\geq 5$  mm from a prior iUPD time point
    - Visible growth of new non-target lesions
    - The appearance of additional new lesions
- Any new factor appears that would have triggered PD by RECIST 1.1

#### *Persistent iUPD*

Progression is considered not confirmed, and the overall response remains iUPD, if:

- None of the progression-confirming factors identified above occurs AND
- The target lesion sum of diameters (initial target lesions) remains above the initial PD threshold (by RECIST 1.1)

Additional imaging for confirmation should be scheduled 4 to 8 weeks from the imaging on which iUPD is seen. This may correspond to the next visit in the original visit schedule. The assessment of the subsequent confirmation imaging proceeds in an identical manner, with possible outcomes of iCPD, iUPD, and iSD/iPR/iCR.

#### *Resolution of iUPD*

Progression is considered not confirmed, and the overall response becomes iSD/iPR/iCR, if:

- None of the progression-confirming factors identified above occurs, AND
- The target lesion sum of diameters (initial target lesions) is not above the initial PD threshold.

The response is classified as iSD or iPR (depending on the sum of diameters of the target lesions), or iCR if all lesions resolve.

In this case, the initial iUPD is considered to be pseudo-progression, and the level of suspicion for progression is “reset”. This means that the next visit that shows radiographic progression, whenever it occurs, is again classified as iUPD by iRECIST, and the confirmation process is repeated before a response of iCPD can be assigned.

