### 13.4. Response Criteria

#### 13.4.1. Evaluation of Target Lesions

Complete Response (CR). Disappearance of all target lesions. Any pathological lymph nodes (whether target or non-target) must have reduction in short axis to <10 mm (<1 cm).

Partial Response (PR). At least a 30% decrease in the sum of the diameters of target lesions, taking as reference the baseline sum diameters.

Progressive Disease (PD). At least a 20% increase in the sum of the diameters of target lesions, taking as reference the smallest sum on study (this includes the baseline sum if that is the smallest on study). In addition to the relative increase of 20%, the sum must also demonstrate an absolute increase of at least 5 mm (0.5 cm). (**Note**: the appearance of 1 or more new lesions is also considered progressions).

Stable Disease (SD). Neither sufficient shrinkage to qualify for PR nor sufficient increase to qualify for PD, taking as reference the smallest sum diameters while on study.

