**V7.0 incorporating Amendment 6, 26Oct2023**

If any of the events above occur, the overall response for that visit is iUPD, and the iUPD evaluation process (see Assessment at the Confirmatory Imaging above) is repeated. Progression must be confirmed before iCPD can occur.

The decision process is identical to the iUPD confirmation process for the initial PD, with one exception: if new lesions occurred at a prior instance of iUPD, and at the confirmatory imaging the burden of new lesions has increased from its smallest value (for new target lesions, the sum of diameters is  $\geq 5$  mm increased from its nadir), then iUPD cannot resolve to iSD or iPR. It will remain iUPD until either a decrease in the new lesion burden allows resolution to iSD or iPR, or until a confirmatory factor causes iCPD.

Additional details about iRECIST are provided in the iRECIST publication (Seymour, 2017).

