4.9.3 Primary Efficacy Endpoint Analysis

The primary efficacy endpoint for Phase 2a is the ORR per RECIST 1.1 and iRECIST as determined by the Investigator.

ORR per RECIST 1.1 is defined as the proportion of subjects with confirmed CR or confirmed PR as BOR in efficacy evaluable analysis set.

iORR per iRECIST is defined as the proportion of subjects with iCR or iPR as BOR in efficacy evaluable analysis set.

Exact two-sided 95% CIs for the ORR/iORR will be calculated using Clopper-Pearson method.

A test from the Simon minimax design for null hypothesis ORR/iORR proportion 4% vs alternative hypothesis 21% will be conducted in each Phase 2a Arm: Arm I, II, III, IV, IVa, V, and Va at 1-sided alpha = 0.025 and the p-value reported.

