4.9.4.3 Duration of Response and Progression Free Survival per investigator

DoR per RECIST 1.1

For subjects who achieve confirmed CR or PR as BOR, DoR is defined as the time (months) from the date of the first CR/PR to the date of the documented disease progression or death, whichever occurs first. The subjects without progression and alive will be censored according to censor rule.

Censoring rules for DoR are the same as those of PFS (Table 4).

iDoR per iRECIST

For subjects who achieve iCR or iPR as BOR, iDoR is defined as the time (months) from the date of the first iCR/iPR to the date of the first iUPD that is followed by iCPD without interruption by iSD/iPR/iCR or death, whichever occurs first. The subjects without iCPD and alive will be censored on the date of last assessment (including iUPD). Censoring rules for DoR are the same as those of PFS (Table 5).

DoR/iDoR median values and its two-sided 95% CIs will be estimated using Kaplan-Meier (KM) method. The DoR/iDoR event-free rates at 3 and 6 months if applicable and the associated two-sided 95% CIs will also be estimated using KM method.

Progression free survival (PFS) per RECIST 1.1

PFS is defined as the time (months) from the date of the first dose of study drugs to the date of the documented disease progression or death, whichever occurs first. The subjects without progression and alive will be censored on the date of last assessment.

Progression free survival (PFS) per iRECIST

iPFS is defined as the time (months) from the date of the first dose date of study drugs to the date of the first iUPD that is followed by iCPD without interruption by iSD/iPR/iCR or death, whichever occurs first. The subjects without iCPD and alive will be censored on the date of last assessment (including iUPD).

PFS/iPFS median values and its two-sided 95% CIs will be estimated using KM method. The PFS/iPFS event-free rates at 3 and 6 months if applicable and the associated two-sided 95% CIs will also be estimated using KM method.

PFS/iPFS of each DL in Phase 1a and each arm in Phase 2a will be plotted with KM curve.

Table 4 Censoring and Event rules for DoR and PFS per RECIST 1.1

Situation	Date of Progression or Censoring	Outcome
No PD or death at the time of data cutoff	Date of last adequate disease assessment	Censored
Start a new anti-cancer therapy before death or PD	Date of last adequate disease assessment prior to the date of new anti-cancer therapy	Censored

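### Under Appendix A, a first unconfirmed progression caused only by a new or non-target lesion becomes iSD or iPR, labelled pseudo-progression, when the lesion is merely unchanged

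*Protocol*

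**What the plan says.** Protocol 13.4.1 notes that "the appearance of 1 or more new lesions is also considered progressions". In Appendix A (Assessment and Decision at RECIST 1.1 Progression), the first visit with RECIST 1.1 progression "will be assigned a visit (overall) response of iUPD, regardless of which factors caused the progression".

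At the confirmatory scan Appendix A allows three outcomes:

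- **Confirmation of Progression (iCPD).** A factor behind the iUPD has worsened, or a new RECIST 1.1 progression factor has appeared.
- **Persistent iUPD.** No confirming factor, and "The target lesion sum of diameters (initial target lesions) remains above the initial PD threshold (by RECIST 1.1".
- **Resolution of iUPD.** No confirming factor, and "The target lesion sum of diameters (initial target lesions) is not above the initial PD threshold". The visit becomes iSD or iPR according to the target sum; only iCR requires every lesion to have resolved. The iUPD is then called pseudo-progression and the suspicion of progression is reset.

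For iUPD episodes after a resolution, the end of Appendix A adds one exception. If new lesions were present at an earlier iUPD and their burden has since increased from its smallest value, the visit cannot resolve to iSD or iPR: "It will remain iUPD until either a decrease in the new lesion burden allows resolution to iSD or iPR".

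SAP 4.9.1 takes visit responses from the investigator under Appendix A. In SAP 4.9.3, "iORR per iRECIST is defined as the proportion of subjects with iCR or iPR as BOR in efficacy evaluable analysis set". In SAP 4.9.4.3 the iPFS and iDoR progression date is that of "the first iUPD that is followed by iCPD without interruption by iSD/iPR/iCR". Protocol 15.1 and SAP 1.4 plan to explore the pseudo-progression rate and base Go/No Go on iRECIST.

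**The concern.** iUPD can be triggered by three kinds of finding, but once worsening is excluded only one of them, the target sum, decides whether iUPD persists or resolves. When the trigger was a new lesion or non-target progression alone, the deciding quantity was never abnormal. A lesion that is still present and unchanged is then recorded as pseudo-progression that has resolved.

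What depends on this:

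- **Pseudo-progression rate.** The SAP gives no separate definition, so Appendix A's label is the only one available, and it would count persisting lesions.
- **iDCR.** A subject whose initial scan on study shows a new lesion that then does not change can count as disease control.
- **iPFS and iDoR.** The intervening iSD or iPR breaks the iUPD-to-iCPD sequence and moves the event later.
- **iORR and the Go rule.** These are reached only if the targets have also shrunk by at least 30% and the response is confirmed.

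**Working it through.** **1. The rules applied to each trigger at the confirmatory scan**

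The last column shows what would follow if resolution also required the triggering new or non-target finding to have resolved.

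| Trigger and finding | Appendix A as written | Trigger must also resolve |
|---|---|---|
| Target sum, unchanged | iUPD | iUPD |
| Target sum, back below threshold | resolved | resolved |
| New lesion only, unchanged | **resolved (iSD/iPR)** | iUPD |
| New lesion only, gone | resolved | resolved |
| New lesion only, grown | iCPD | iCPD |
| Non-target only, unchanged | **resolved (iSD/iPR)** | iUPD |
| Non-target only, no longer progression | resolved | resolved |
| Non-target only, grown | iCPD | iCPD |
| Target and new lesion; target falls, new lesion unchanged | **resolved (iSD/iPR)** | iUPD |

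Three of the nine cases differ. For a trigger that is new-lesion-only or non-target-only, persistent iUPD cannot be reached. If the target sum stays below the threshold the visit resolves; if it crosses the threshold, that is a new progression factor and the visit is iCPD.

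**2. Does other text close the gap?**

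- The worsening check covers growth of new and non-target lesions and additional new lesions. It does not catch persistence without growth.
- The later-episode exception is written as a departure from the process for the initial progression. It needs an increase in new-lesion burden and does not mention non-target lesions.
- The section on progression after pseudo-progression resolves itself provides for non-target progression that remains unresolved. So resolution in this appendix does not imply that the trigger has gone.

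**3. Effect on iDCR and iPFS, using the planned scan times (illustrative subject)**

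Scans fall every 6 weeks, and a 6-week gap lies within the 4-to-8-week confirmation window.

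- Week 6: new lesion, targets stable: iUPD.
- Week 12: unchanged: iSD as written. This exceeds the 4-week minimum for SD, so best response is iSD and iDCR counts a success.
- Week 18: new lesion grows enough to qualify: iUPD again, because suspicion was reset.
- Week 24: further growth: iCPD.

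As written, the iPFS event is dated week 18. If week 12 had stayed iUPD, the growth at week 18 would be iCPD and the event would be dated week 6. The shift is 18 − 6 = 12 weeks. If there were no scan after week 18, the same subject would be censored at week 18 instead of having an event at week 6.

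**4. The design that iORR feeds**

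Inputs: 17 then 8 evaluable subjects (25 in all), Go on at least 1 response in 17, 4% vs 21%, one-sided alpha 0.025, 80% power (protocol 15.1; SAP 1.4 and 2.9.1). The documents do not print the final boundary. A minimax search gives rejection at 4 or more of 25.

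P(Go) = 1 − (1 − q)^17

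P(reject) = Σ over x = 1 to 17 of Bin(x; 17, q) × P(Bin(8, q) ≥ 4 − x)

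At q = 0.21, P(reject) = 0.8001, so the stated 80% is reproduced. At q = 0.04, P(reject) = 0.0164.

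Now let q = 0.04 plus an **assumed** share of subjects reclassified to confirmed iPR:

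| Added share (assumed) | q | P(Go) | P(reject) |
|---|---|---|---|
| 0 | 0.04 | 1 − 0.96^17 = 0.500 | 0.016 |
| 2 points | 0.06 | 1 − 0.94^17 = 0.651 | 0.059 |
| 4 points | 0.08 | 1 − 0.92^17 = 0.758 | 0.135 |

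The documents supply no value for the added share.

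**The case against.** The strongest reply is that the convention may be deliberate. The appendix keeps new-lesion sums separate from the baseline target sum, requires all lesions to resolve only for iCR, and follows known new lesions from their nadir after a resolution. That reads like a response rule that tolerates stable residual lesions. It also defers details to the iRECIST publication, which is not available here, so no claim is made that Appendix A departs from it. This stands, and it argues for a supplementary analysis rather than replacing the investigator's response. It does not explain why the same finding, no change, is iUPD for one lesion type and pseudo-progression for another.

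Other mitigations also stand. RECIST 1.1 ORR is reported beside iORR, and a new lesion is progression there. An iPR needs a 30% target reduction and confirmation at 4 weeks or more. Arms IV and V are complete, and Arms IVa and Va have no interim analysis, so no Go decision remains to be made in those four arms.

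Three stronger readings are tempting and are not supported:

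- **That resolution looks at the target sum alone.** The worsening check does read new and non-target lesions; it misses only persistence without growth.
- **That the later-episode exception already demands a decrease whenever new lesions persist.** It applies only after their burden has increased, so it is no precedent for unchanged lesions.
- **That the excess of iRECIST over RECIST 1.1 responders (3/27 vs 1/27 in Arm IV, 2/26 vs 1/26 in Arm V; protocol 2.3) shows the defect at work.** Protocol 2.3 calls the Arm IV RECIST 1.1 response confirmed but does not say so of the iRECIST responses. The gap could reflect confirmation status or a genuine target flare that regressed. Nothing shows a persisting trigger lesion.

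**Conclusion.** The point holds as a gap in the classification rule. A first iUPD caused only by a new or non-target lesion and unchanged at the next scan must be recorded as iSD or iPR and as pseudo-progression. This follows from Appendix A's own text.

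The main exposure is the pseudo-progression rate, iDCR and the iPFS/iDoR dates. iORR and the Go rule are exposed less often, through confirmed mixed responses. How many subjects are affected cannot be learned from the documents. The Simon figures show sensitivity under assumed additions of 2 and 4 points, each treated as a confirmed iPR. They are not an estimate of inflation in this trial.

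**What to change.** In SAP 4.9.2.2, with a cross-reference in 4.9.4.3, prespecify a supplementary derivation and leave the investigator-reported visit response as it is:

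- A visit stays iUPD if the triggering new lesion is still present without decrease, or if the triggering non-target progression is still recorded as progression. The SAP should define decrease: for measured new lesions from their separately kept sum of diameters, for the others from the recorded status.
- Such a visit does not count as iSD or iPR for best response, as pseudo-progression, or as an interruption in iPFS/iDoR.
- Report iORR, iDCR, the pseudo-progression rate, iPFS and iDoR both ways.
- Give the number of iORR and iDCR successes, and of labelled pseudo-progressions, whose triggering lesion persisted.

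The sponsor must also reconcile three parts of Appendix A: Persistent iUPD, Resolution of iUPD, and the closing section on progression after pseudo-progression with its exception. Table 6 ties imaging and treatment to these categories, so no clinical rule is proposed here.

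The cost is SAP wording and some programming; SAP 4.9.4.3 already lists target, non-target and new-lesion data. iDCR, iORR and iPFS may look slightly less favourable in the supplementary version.
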